8.6 PHARMACODYNAMICS

Ki67 is a marker of cellular proliferation and has shown value as a predictor of benefit from treatment and of long-term outcome. Change in Ki67 is the primary endpoint. Ki67 will be evaluated in tumor tissue by IHC (See [Section 8.6.1](#) for details). Ki67 index will be recorded independently by 2 histopathologists blinded to treatment allocation.

For additional parameters, please see [Section 8.7](#) and [Section 8.8](#).

8.6.1 Tumor biopsy

Determination of tumor characteristics (HER2 status by IHC or FISH, ER and PgR by IHC, Ki67 by IHC, etc) on the diagnostic biopsy specimen based on local laboratory results serves for participant selection. For clinical sites reporting Ki67 expression by range rather than a single value, a local re-evaluation might be requested to confirm Ki67 expression $\geq 15\%$.

During the study, tumor biopsy will be performed at the time points described in SoA (Section 1.3), and the assessment window is not impacted by dose omission. Biopsy samples will be examined for Ki67, DNA mutation analysis, RNA expression analysis, and protein analysis (eg, ER, PgR, BCL2, Cyclin D1) in central laboratory. Ki67 index will be recorded independently by 2 histopathologists blinded to treatment allocation. Complete Cell Cycle Arrest (CCCA: Ki67 $\leq 2.7\%$) will be evaluated. Additional protein expression assessments by digital method will be performed for some biomarkers (eg, Ki67).

- A fresh core-cut biopsy sample will be collected prior to the first dosing of IMP serving as baseline value. It is recommended that the baseline biopsy should be performed after the eligibility is confirmed, if possible. The baseline biopsy may be performed any time prior to the initiation of study treatment. Alternatively, biopsy tissue from the diagnostic biopsy may be used as baseline sample if the following criteria are fulfilled:
 - There is sufficient material available for biomarker analysis (a minimum of 7 x 5- μ m sectioned FFPE slices on slides are required); AND
 - Diagnostic biopsy performed within 4 weeks prior to randomization; AND
 - No hormone replacement therapy (HRT) administered from 30 days prior to diagnostic biopsy till screening; AND
 - No anticancer treatment administered between diagnosis and screening.
- Post-treatment core-cut biopsy samples will be collected on the excised tissues during surgery. The surgery should be performed on Day 15 (+1). If surgery is delayed for any reason, every effort should be made to perform a new tumor core-cut biopsy within 48 hours maximum after last IMP dose. If a new tumor core-cut biopsy within 48 hours maximum after last IMP dose is not performed, nevertheless it is recommended to collect post-treatment core-cut biopsy samples on the excised tissues during the planned surgery. Post-treatment biopsy samples should be collected in the same area as for baseline biopsy as far as possible.

For both the baseline pre-treatment and the post-treatment biopsy samples, a tissue block is preferred for the central analysis. If tissue sections are provided instead, it is preferred to have approximately at least 9 x 5- μ m and 5 x 10- μ m sections on slides, though a smaller number of slides for the baseline sample are acceptable, if necessary (see above for minimum requirement).

Pre-treatment and post-treatment biopsy samples will be fixed in neutral-buffered formalin for 24-72 hours prior to processing and embedding at local pathology centers. These biopsy samples will be sent for analyses to a central laboratory.

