AE = adverse event, cfDNA = cell free DNA, DMET = Drug metabolizing enzymes and transporters, eCRF = electronic case report form, ECG = electrocardiogram, ECOG PS = Eastern Cooperative Oncology Group Performance Status, IMP = investigational medicinal product, IRT = Interactive response technology, pCR = pathological complete response, PEPI = Preoperative Endocrine Prognostic Index, PK = pharmacokinetic, pN = pathological node, pT = pathological tumor, QD = once daily, SAE = serious adverse event

- a Procedure:** Assessments to be performed prior to study treatment administration unless otherwise indicated. Informed consent should be signed before any study specific procedures. It can be signed more than 14 days prior to randomization. Screening time indicates in which timeframe exams used to support eligibility have to be done prior to randomization. All the tests or procedures scheduled on D1 should be done at predose time unless otherwise stated.
- b D1** refers to the day the participant receives the initial dose of study treatment which will be a single administration of amcenestant 400 mg or 200 mg QD, or letrozole 2.5 mg QD.
- c Surgery:** The date of surgery should be fixed before randomization takes place. The time between first IMP administration and surgery should be of 14 days and the last dose is planned to be taken the day before surgery. Surgery should be done 1 day after the last IMP administration; however this could exceptionally be extended to a maximum of 48h after last IMP administration. In case of a longer unexpected surgery delay (>48 hours from last IMP administration), all efforts should be done to perform a tumor biopsy no more than 48 hours of last IMP administration.

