5.2 EXCLUSION CRITERIA

Participants are excluded from the study if any of the following criteria apply:

Medical conditions

E 01. Medical history or ongoing gastrointestinal disorders potentially affecting the absorption of amcenestant or letrozole. Participants unable to swallow normally and to take capsules or tablets. Predictable poor compliance to oral treatment. Participants with known active hepatitis A (positive HA antigen or positive IgM); B (either positive HBs antigen or positive hepatitis B viral DNA test above the lower limit of detection of the assay); C (positive hepatitis C antibody result or quantitative hepatitis C (HCV) ribonucleic acid (RNA) results greater than the lower limits of detection of the assay) infection; or hepatic cirrhosis.

E 02. Participant with any other cancer. Adequately treated basal cell or squamous cell skin cancer or in situ cervical cancer or any other cancer from which the participant has been disease free for >3 years are allowed.

E 03. Evidence of metastatic spread by standard assessment according to local practice.

Prior/concomitant therapy

E 04. Treatment with strong CYP3A inducers within 2 weeks before first study treatment administration or 5 elimination half-lives whichever is longest and cannot be replaced.

E 05. Deleted in Protocol Amendment 02.

- E 06. Treatment with drugs that are sensitive substrates of P-glycoprotein (P-gp) (dabigatran, digoxin, fexofenadine) or of breast cancer resistance protein (BCRP) (rosuvastatin, sulfasalazine) within 2 weeks before first study treatment administration or 5 elimination half-lives whichever is longer.
- E 07. Use of any investigational agent within 4 weeks prior to randomization.
- E 08. Recent use of hormone replacement therapy (last dose ≤ 30 days prior to randomization).
- E 09. Prior anti-cancer treatment is not allowed unless it was completed at least 1 year prior to inclusion into this trial.

Prior/concurrent clinical study experience

- E 10. Previous systemic or local treatment for the new primary breast cancer currently under investigation (including surgery, radiotherapy, cytotoxic and endocrine treatments).

Diagnostic assessments

- E 11. Inadequate hematological function including neutrophils $< 1.5 \times 10^9/L$; platelet count $< 100 \times 10^9/L$, hemoglobin < 8.0 g/dL.

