6.5 CONCOMITANT THERAPY

Any medication or vaccine (including over-the-counter or prescription medicines, vitamins, and/or herbal supplements or medicine) that the participant received within 30 days prior to randomization or receives during the study must be recorded in the eCRF along with:

- Reason for use
- Dates of administration including start and end dates

Participants must abstain from taking prescription or nonprescription drugs (including vitamins and dietary or herbal supplements) during 14-day treatment if the drug is a potential enzyme inducer or 5 half-lives (whichever is longer) before the start of study intervention until completion of the follow-up visit, unless, in the opinion of the Investigator and Sponsor, the medication will not interfere with the study.

Concomitant medication may be considered on a case-by-case basis by the Investigator.

Any medication which is considered necessary for the participant's welfare, and which is not expected to interfere with the evaluation of the study drug, may be given at the discretion of the Investigator, except for those listed below.

Any anti-cancer medications (other than the study treatment) and hormone replacement therapy/hormonal contraception are prohibited from the date of informed consent to the end of study treatment.

The following therapies/medications are prohibited throughout the active treatment phase for the amcenestant treatment arms:

- The concomitant use of drugs that are strong inducers of CYP3A since they may decrease amcenestant exposure (See [Section 10.8](#)).
- Herbal medications and food supplements including St John's Wort and genistein during treatment period since they could decrease amcenestant exposure.
- The concomitant use of drugs that are sensitive substrates of P-gp (dabigatran, digoxin, fexofenadine) or BCRP (rosuvastatin, sulfasalazine), since amcenestant is a potential inhibitor of P-gp and BCRP and may increase their absorption.
- The concomitant use of drugs that have UGT inhibition potential and are contraindicated with UGT substrates, including but not limited to atazanavir and probenecid, since amcenestant is substrate of UGT1A1 and UGT1A4.

Special caution should be taken with regards to the following therapies for the amcenestant treatment arm:

- Proton Pump Inhibitors (PPI) (ie, omeprazole): when prescribed, amcenestant intake should be preferred with food.

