Section 5.1 Inclusion criteria	In I05, "A breast tumor size of at least 10 mm in short axis measured by ultrasound" was replaced by "A breast tumor size of at least 10 mm in greatest dimension measured by ultrasound"	According to AJCC Cancer Staging Manual 8th edition 2017, the size of tumor refers to the greatest dimension.
Section 5.2 Exclusion criteria	E08, "Currently receiving (and unwilling to discontinue) hormone replacement therapy (last dose < 14 days prior to randomization)" was replaced by "Recent use of hormone replacement therapy (last dose ≤ 30 days prior to randomization)"	Discontinuing HRT could have impact on the tumor including analysis of key biomarkers such as Ki67. So the washout duration of HRT should be at least 30 days prior to randomization.
Section 5.2 exclusion criteria	"E16 Men" was deleted.	It's a duplicated information with I10

[figure not shown]
Section # and Name	Description of Change	Brief Rationale
Section 5.2 exclusion criteria; Section 6.5 Concomitant therapy	New exclusion criteria E21 added. And drugs that are potential inhibitors of UGTs are moved to the list of prohibited therapies/medications	To be in line with the IB of SAR439859, drugs that are potential inhibitors of UGTs are added to the exclusion criteria and the list of prohibited therapies/medications.
Section 5.3 lifestyle consideration; Section 6.5 concomitant therapy	The duration of sun protection for patients taking SAR439859 was extended from "during study treatment" to "during study treatment and for at least 5 days after discontinuation of SAR439859"	SAR439859 is expected to be eliminated from plasma after 5 times plasma half-life (approximately 24 hours). So, it is recommended that sun screen should be used during the treatment and at least 5 days after discontinuation of SAR439859.
Section 6.6 Dose modification	Dose modification criteria for SAR439859 and letrozole was modified to not allow any dose modification or reintroduction of study treatment for NCI CTCAE Grade ≥ 3 AEs.	There is no justification to re-challenge SAR439859 or letrozole to a patient after the first occurrence of Grade ≥ 3 AE considering the short period of treatment (ie, 14 days) while in addition no direct benefit is intended to the patient in this study.
Section 8.3 AE and SAE	"symptomatic overdose has to be reported as a standard AE." replaced to "asymptomatic overdose has to be reported as a standard AE."	Error correction

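### The 30-day HRT washout is not tied to a fresh baseline biopsy, so a compliant baseline Ki67 can be taken inside the washout

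*Protocol*

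**What the plan says.** **Reason for the washout.** Protocol Appendix 15 (Amendment 01) explains the E08 change: "Discontinuing HRT could have impact on the tumor including analysis of key biomarkers such as Ki67".

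**Eligibility.** E08 in Protocol 5.2 excludes "Recent use of hormone replacement therapy (last dose ≤ 30 days prior to randomization"). The anchor is randomization. I04 b in 5.1 expressly admits women who have stopped HRT.

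**Baseline sample.** Protocol 8.6.1 allows two routes. Re-used diagnostic tissue must meet several conditions, including "No hormone replacement therapy (HRT) administered from 30 days prior to diagnostic biopsy till screening". The default route, a fresh core biopsy, carries no HRT condition: "The baseline biopsy may be performed any time prior to the initiation of study treatment". The only steer on timing is advisory: "It is recommended that the baseline biopsy should be performed after the eligibility is confirmed, if possible". Footnote d of the Schedule of Activities (SoA) repeats this.

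**Related limits.** Protocol 6.5 states that "hormone replacement therapy/hormonal contraception are prohibited from the date of informed consent to the end of study treatment". SoA footnote a adds "Informed consent should be signed before any study specific procedures", and of consent says "It can be signed more than 14 days prior to randomization", with no upper limit.

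**Per-protocol set.** The HRT exclusion in SAP 2.3.3 uses the same interval before randomization as E08. A separate item there excludes anyone given a prohibited medication.

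**The concern.** If stopping HRT can change Ki67, the interval to protect is the one between the last HRT dose and the biopsy that supplies the baseline value. The protocol does this for diagnostic tissue and leaves it undone for the fresh sample, which is its default.

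For a woman biopsied early in the washout, the change from baseline to Day 15 may combine HRT withdrawal with the study drug. That would enter the per-arm percentage reduction, the waterfall plot and the ≥50% decrease rate, and would add some variance. These summaries matter more now: SAP 2.4 drops hypothesis testing because enrollment ended early, and confidence intervals are descriptive only.

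The planned sensitivity analysis would not show the problem, because the per-protocol HRT rule shares the randomization anchor. The data may not show it either. Protocol 6.5 requires medications to be recorded from 30 days before randomization, and SAP 2.1.2 describes collection from consent. An eligible, compliant former user took her last dose before both. The SoA line on previous medications states no look-back period.

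**Working it through.** **1. Interval guaranteed at a fresh biopsy.** E08 excludes a last dose 30 days or less before randomization, so an eligible woman is at least 31 days off HRT at randomization. For a biopsy k days before randomization, the shortest HRT-free interval is 31 − k days:

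| k (days before randomization) | 0 | 1 | 7 | 14 | 28 | 30 |
|---|---|---|---|---|---|---|
| Shortest interval (days) | 31 | 30 | 24 | 17 | 3 | 1 |

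If the SoA screening column (up to 14 days) is taken to bind the biopsy, 17 days are assured, not 30. If 8.6.1 is read as written, the floor is 1 day, because HRT is barred from the date of consent and consent comes before the biopsy.

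**2. A compliant case.** Last HRT dose Day -32, consent Day -31, fresh biopsy Day -30, randomization Day 0.
- E08: 32 days off HRT at randomization; passes.
- 6.5: no HRT on or after consent; passes.
- SoA footnote a: consent precedes the biopsy and may be more than 14 days before randomization; passes.
- SAP 2.3.3: neither the HRT item nor the prohibited-medication item applies, so she stays in the per-protocol set.
- HRT-free interval at baseline: 32 − 30 = 2 days. Diagnostic tissue with the same interval would be refused.

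**3. The plan's own power.** Inputs from Protocol 9.2: 40 evaluable per arm, log-scale SD 1, difference −0.693, Hochberg at one-sided 2.5%. Simulating 100,000 trials with pairwise t-tests gives 84.8% marginal and 91.5% disjunctive power, against 85% and 91.5% stated.

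**4. Effect of withdrawal falls.** Assumptions, none from the documents: a share p = 5-20% of every arm is biopsied inside the washout, and in each such patient Ki67 falls by a further f = 30-50%, additive on the log scale.

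- Arm residual Ki67 becomes planned residual × (1 − f)^p. At the low end, 0.7^0.05 = 0.982; at the high end, 0.5^0.20 = 0.871.
- Letrozole: 1 − 0.30 × 0.982 = 70.5% to 1 − 0.30 × 0.871 = 73.9% (planned 70%).
- Amcenestrant: 1 − 0.15 × 0.982 = 85.3% to 1 − 0.15 × 0.871 = 86.9% (planned 85%).
- The ≥50% decrease rate is (1 − p)Φ(ln 0.5 − ln m) + pΦ(ln 0.5 − ln m − ln(1 − f)), with m the planned residual. Letrozole goes from 69.5% to 70.1-73.3%; amcenestrant from 88.6% to 88.8-90.3%.
- Between-arm ratio: the factor (1 − f)^p cancels, so 0.15/0.30 = 0.50 in every scenario.
- SD is √(1 + p(1 − p)[ln(1 − f)]²), at most √(1 + 0.16 × 0.480) = 1.04.
- Simulated marginal power falls from 84.8% to 82.1-84.4%, and disjunctive power from 91.5% to 89.5-91.3%.
- With no drug difference (10% affected, 50% fall), simulated overall type I error is 2.3%, so it is not inflated.

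**5. Chance imbalance.** The SD it adds to the log difference is √(2p(1 − p)/40) × |ln(1 − f)| = 0.02 to 0.06, against a planned standard error of √(2/40) = 0.22. If 5 of 40 v 1 of 40 were affected with a 50% fall, the ratio would move by exp((4/40) × ln 0.5) = 0.93.

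**The case against.** Four objections deserve weight.

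**HRT intake at biopsy.** A reader might infer that a fresh biopsy can be taken while the woman is still on HRT. The documents do not support this. HRT is barred from the date of consent, consent precedes study procedures, and a dose on or after consent would also trigger the per-protocol exclusion for prohibited medication. Only a residual effect after the last dose is possible, and the documents give no duration for it beyond the 30-day rule. The objection stands, and it limits the point to biopsies taken inside the washout.

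**Bias in the treatment comparison.** A reader might also infer that HRT withdrawal biases amcenestrant against letrozole. It does not. Allocation is randomized 1:1:1, so any withdrawal fall is balanced in expectation. Chance imbalance is sampling error, not bias. This stands too.

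**Size.** An affected patient's own log shift, ln 0.5 = −0.693 for a 50% fall, equals the planned between-arm difference. It is tempting to set the two side by side, but one is a single patient's change and the other a difference in means. The like-for-like quantity is the arm shift, p × |ln(1 − f)|, at most 0.20 × 0.693 = 0.14 in the scenarios above, and it applies to all arms.

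**Existing mitigation.** The SoA puts the biopsy in the 14-day screening column, SAP 2.1.6.2 calls it a screening sample, and biopsy after confirmed eligibility is recommended. If followed, these give at least 17 days and often close to 30. They do not bind: 8.6.1 permits any time before first dose, the recommendation applies only where possible, and SoA footnote a relates the window to examinations that support eligibility, whereas selection uses the local diagnostic biopsy.

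**Conclusion.** The gap in the text is certain. A fresh baseline biopsy can comply with every HRT rule and still fall inside the washout that the protocol adopted to protect Ki67, and the per-protocol set does not remove it. The consequence is confined to within-arm Ki67 results and some extra variance; the amcenestrant-letrozole ratio is unbiased in expectation.

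The magnitude is unknown, because neither the number of former HRT users nor the withdrawal effect is given. It is probably small. Under the assumed ranges, the within-arm reduction moves by at most about 4 percentage points for letrozole (70% to 73.9%) and 2 for amcenestrant (85% to 86.9%), and marginal power falls by less than 3 points. The power figures describe the planned 40 per arm. Enrollment ended before that, so chance imbalance could weigh somewhat more in the actual data. The point is worth acting on because the remedy uses the sponsor's own rule and costs little, not because the primary contrast is in doubt.

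**What to change.** **Protocol 8.6.1 and SoA footnote d.** Apply the existing HRT condition for diagnostic tissue to whichever biopsy serves as baseline, fresh or diagnostic. This adds no biopsy. Eligible women are already at least 31 days off HRT at randomization, so a sample taken on that day, or in the up to 3 days before first dose, meets the condition without added waiting. There is no need to carry over the 4-week age limit for diagnostic tissue; if it is wanted, it must be reconciled with the 14-day screening column.

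**SAP 2.3.3.** Anchor the per-protocol HRT exclusion to the baseline biopsy as well as to randomization.

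**Data and sensitivity analysis.** Retrieve the date of last HRT dose for former users so that the HRT-to-biopsy interval can be computed. Report how many baselines fall inside the washout, and repeat the primary and ≥50% decrease analyses without them.

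Because enrollment has ended, a protocol edit protects no further patient in this trial. The SAP change and the data retrieval are what remain usable, and should be settled before database lock.

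**Cost.** One sentence in each document, one data query and one extra analysis. The downside is slightly less freedom in timing the biopsy and possibly a few more per-protocol exclusions.

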8.7 GENETICS

Genetic analysis of tumor biopsies and cell-free DNA (cfDNA) will be performed in this study.

Cancer gene mutations present in the tumor prior to treatment might influence the response to amcenestant. The presence of gene mutations in tumor DNA may be assessed through

- A) Mutation analysis of DNA isolated from a tumor biopsy, and
- B) Mutation analysis of cfDNA isolated from plasma.

Both biopsies and cfDNA samples will be collected pre-treatment and post treatment. These analyses will focus on genes that may increase understanding of disease subtypes, the biology of cancer and related conditions, how the body handles amcenestant, and drug response and toxicity, and possibly to identify new drug targets or biomarkers.

In addition, saliva will be collected pre-treatment as a source of normal reference DNA for comparison with the tumor-derived DNA data. Sequencing may be performed on the DNA from the saliva sample. In the event of technical issues affecting the sample, a replacement genetic saliva DNA sample may be requested from the participant.

At the study visit as specified in the SoA ([Section 1.3](#)), a blood sample will be collected only in amcenestant treatment arms to investigate allelic variants of drug metabolizing enzymes (for example variants of UGT1A1 and UGT1A4), drug transporters and/or other ADME related genes as intrinsic factors associated with PK or PD variability of amcenestant. This sample will be used for this specific analysis and not for other future research.

Special procedures for collection, handling, storage, and shipment will be described in a separate laboratory manual which will be available at the investigational site.

Samples may be stored for a maximum of 15 years (or according to local regulations) following the last participant's last visit for the study at a facility selected by the Sponsor to enable additional analysis of DNA biomarkers to increase understanding of amcenestant and/or cancer or related diseases, and potentially to identify new drug targets or biomarkers.

See [Section 10.5](#) (Appendix 5) for Information regarding genetic research. Details on processes for collection and shipment of these samples can be found in the laboratory manual.

